III. INTERVENTION

The intervention consists of a 16 week internet-based health coaching intervention. All participants (both groups) will interact with the BIAPAMS website weekly, and have one-on-one video chats with a health coach in weeks 1-12, 14, and 16. In addition to the BIPAMS website, participants in the BIPAMS+Diet group will be asked to log their food intake using a mobile app, beginning in week 9. All participants (both groups) will work toward physical activity goals focused on increasing daily steps. In addition to these goals, participants in the BIPAMS+Diet group will be given weekly dietary goals related to intake of various food groups each week, beginning in week 9. All goals are individualized the participant and therefore will be different for each participant.

The intervention consists of 3 components: the BIPAMS website (both groups), HealthWatch 360 mobile/desktop app (BIPAMS+Diet group only), and One-on-One video chats (both groups). All participants will receive the standard BIPAMS intervention for the first 8 weeks of the trial. At the completion of the eighth week, participants will receive their randomization assignment. Those in the BIPAMS+Diet arm will begin receiving dietary materials in week 9. Those in the comparison group (BIPAMS) will continue receiving the established BIPAMS intervention for the remainder of the trial.

We have chosen to structure the intervention in this way for two reasons. First, persons with MS often report symptom burden as reasons for difficulty in establishing new health behaviors. For this reason, initiating multiple behaviors simultaneously may be more difficult for this group than the general population. By initiating physical activity first, we hope to maximize participants' adherence to the recommendations by reducing the potential psychosocial and physical stressors of concurrent behavior changes. Secondly, starting with the portion of the intervention that has already been established as efficacious will allow us to use the first 8 weeks as a run-in period and better differentiate the effects of the combined approach of diet and exercise compared to the exercise-alone intervention.

- 1. BIPAMS Website: The Internet website represents a medium for disseminating information on the skills, techniques, resources, and strategies for becoming and staying physically active with MS. The behavioral intervention does not provide a prescription for exercise or physical activity itself (i.e., the program does not specifically recommend mode, duration, frequency, or intensity of movement). The primary content of the Internet website is based on SCT and represents the transformation of an effective and empirically validated, face-to-face intervention approach that increased adherence with supervised exercise training in middle-aged adults and persons with MS. The content is delivered through interactive video courses based on E-learning principles (i.e., content and instructional methods delivered on a computer with interactive materials that build knowledge and skills for behavior change). The interactive video courses were developed using Storyline in Articulate 360 (Articulate, New York, NY) based on operationalizing principle elements of SCT including self-efficacy, outcome expectations, impediments, and goal-setting. The interactive video courses follow a similar template of Introduction and Overview, Primary Content, and Take Home Message. The interactive video courses received formative evaluation from representative persons with MS and are organized into four “Modules” for the behavioral intervention, namely Getting Started; Planning for Success; Beating the Odds; and Sticking with It. The Getting Started module includes interactive video courses on the benefits of physical**

activity for persons with MS, instructions for becoming physically active, completing daily activity logs, and self-monitoring of behavior via a Yamax SW-200 pedometer and an embedded website feature called Tracker for reporting weekly physical activity. The *Planning for Success* module includes interactive video courses on goal setting and feedback again via a Yamax SW-200 pedometer and Tracker, developing realistic outcome expectations, and increasing self-efficacy. The *Beating the Odds* module includes interactive video courses on identifying barriers to physical activity and strategies of overcoming barriers as well as developing social support. The *Sticking with It* module includes interactive video courses on maintaining an active lifestyle and prevention of relapse into a sedentary lifestyle. Those interactive video courses are supplemented with embedded options of “Learn More” and “Resources.” The “Learn More” option includes passive videos on content that aligned with the course, and the “Resources” option includes research articles for documenting the statements within the courses; manuals on stretching, aerobic, and resistance modes of physical activity; and worksheets and questionnaires for further developing the personal relevance of the stories. The interactive video courses along with embedded options became “accessible” in a titrated fashion of seven times during the first 2 months, four times during the second 2 months, and twice during the final 2 months of the intervention.

The Tracker feature of the website was designed for self-monitoring and goal-setting within the website itself, and the participants’ data are directly accessible by the behavioral coaches for discussions within the one-on-one video chats. Tracker includes four elements of Ready (directly entering baseline week of step counts), Set (setting a step count goal for the program), Go (directly entering step counts weekly during the program), and See (graphical display of step counts for monitoring progress over the program compared with the goal). This is further supplemented with direct, on-screen feedback regarding progress with the behavioral goal on a weekly basis. We again received formative evaluation from representative persons with MS for refinement of the new Tracker feature.

The website further includes “Voices” of audio files of persons with MS discussing physical activity that were supplemented by a loop of pictures. The “Voices” change weekly and are included for engaging people with MS in social modeling as a source of self-efficacy information based on SCT. The Internet website further includes an ongoing and seeded participant “Forum” for discussions of physical activity behavior change amongst participants (i.e., another form of vicarious experience). The website is supported by automated e-mail announcements about updates and tips of the week, and includes information on News (i.e., late breaking research results) and Events that further support the website content.

In addition to these intervention aspects, which all participants will receive, the BIPAMS+Diet group will access additional information beginning in Week 9. Participants in the BIPAMS+Diet group will receive a calorie prescription intended to create a 500 kcal/day energy deficit, as recommended in current obesity treatment guidelines. Study staff will derive calorie prescriptions from the Harris-Benedict formula, which uses individual data to calculate an individualized prescription. Dietary content will focus on increasing fruit and vegetable intake, consumption of lean protein, reduced-fat dairy, whole grains, and reduction of saturated fat intake. Participants will receive nutrition education content via the BIPAMS website and video chats will consist of discussion of both physical activity and dietary goals. Each participant in this group will be given additional resources that will be provided on the “resources” page, which include information on meal planning, snack ideas, goal setting for dietary behaviors. Participants in the BIPAMS group will be given a single link to healthy eating resources for people with MS from the National MS Society website, but no other healthy eating content will be given and no individualized recommendations or goals will be given related to nutrition. All resources provided from the NMSS website can be found at <https://www.nationalmssociety.org/Living-Well-With-MS/Diet-Exercise-Healthy-Behaviors/Diet-Nutrition>

2. HealthWatch 360: Participants in the BIPAMS+Diet group will be asked to track all food consumption in the HealthWatch 360 mobile app. We will use the research portal available through Healthwatch360 website and app. This allows researchers to track participant entries in

real time and monitor the nutrition goals of participants. The research portal is HIPAA-compliant. Upon completion of the study, the participant may continue to use the HealthWatch 360 application as it is free to the public, but the research portal license will expire so the researchers will no longer be able to track the entries and nutrition goals of the participants. If the participant prefers to remove the application from their mobile device, study staff will assist in the deletion of the program from the mobile device per the application deletion procedure for the specific type of mobile device.

3. **One-on-one Video Chats:** The one-on-one video chats support adherence with the intervention, discussion and elaboration of website material, supportive accountability, and reporting adverse events/injuries; these further provide vicarious experience (i.e., social interaction) for promoting behavior change. The video chats are modeled for maximizing adherence with Internet interventions, provide an ongoing interaction between the behavioral coach and the participant, and are conducted face-to-face through the web-based program Zoom™. The video chats are semi-scripted and based on principles of supportive accountability. The video chats consist of an ongoing review of goal-setting and progress toward goal attainment through Tracker as well as discussion of strategies and facilitators of behavioral change based on SCT and current website content. Supportive accountability, for example, is accomplished by encouraging participants to wear the pedometer daily, and monitor behavioral change and goal attainment throughout the 4-month intervention. The chats occur weekly during the first 3 months (12 total calls), and bi-weekly during the last month (2 total calls) of the intervention.

IV. FOLLOW UP DATA COLLECTION

At the half-way point of the intervention (week 8), participants will be asked to wear the accelerometer again for 1 week, and complete the questionnaires online again. Participants will not be asked to come into the lab at this point. Accelerometers will be mailed to them and questionnaires will only be done online.

At completion of the 16-week intervention, participants will be scheduled to return to Lakeshore Foundation. All baseline testing will be repeated following the same protocols as baseline.

- What is the probable length of time required for the entire protocol (i.e., recruitment through data analysis to study closure)? 1 year.
- What is the total amount of time each participant will be involved? 20 weeks (2 weeks baseline data collection, 16 weeks intervention, 2 weeks follow up data collection)
- If different phases are involved, what is the duration of each phase in which the participants will be involved? If no phases are involved, enter "None." NA
- List the procedures, the length of time the procedure takes, the total # of times the procedure is performed, and indicate whether each is performed solely for research or would already be performed for treatment or diagnostic purposes (routine care) for the population.
-Insert additional table rows as needed.
-If procedure is sometimes research and sometimes routine care, include on separate lines with number of times as each.

Procedure	Length of Time Required of Participants	Total # of Times the Procedure is Performed	Research (Res) –OR– Routine Care
Anthropometrics	15 minutes	2	 Res  Routine
Bloodwork (insulin, glucose, lipids)	10 minutes	2	 Res  Routine
DXA	20 minutes	2	 Res  Routine
Pregnancy Test	5 minutes	2	 Res  Routine

(females of child-bearing age only)			
24 Hour Dietary Recall	3 days	2	 Res  Routine
Timed 25-Foot Walk (T25-FW)	1-5 minutes	2	 Res  Routine
9-Hole Peg Test (9-HPT)	10 minutes or less	2	 Res  Routine
Symbol Digit Modalities Test (SDMT)	Less than 5 minutes	2	 Res  Routine
Expanded Disability Status Scale (EDSS)	20 minutes	1	 Res  Routine
Questionnaires	20-45 minutes	3	 Res  Routine
Accelerometer	7 days	3	 Res  Routine
Video Chats	10-15 minutes	14	 Res  Routine

f. Will an interview script or questionnaire be used? Yes No

If Yes, attach a copy.

g. Will participants incur any costs as a result of their participation? Yes No

If Yes, describe the reason for and amount of each foreseeable cost. There is a potential for participants to incur cell phone and internet data usage charges while using the Healthwatch 360 system or one-on-one video calls.

h. Will participants be compensated? Yes No

If Yes, complete i-v.

i. Type: (e.g., cash, check, gift card, merchandise): Check

ii. Amount or Value: \$50

iii. Method (e.g., mail, at visit): mail

iv. Timing of Payments: (e.g., every visit, each month): At completion of baseline data collection and completion at follow up data collection.

v. Maximum Amount of Compensation per Participant: \$100

18. Benefits

Describe the potential benefits of the research. The benefits to the participants are potentially numerous. The physical and psychological benefits that reliably result from regular physical activity and following a healthy diet far outweigh the minimal risks. Beyond the common physical and psychological benefits, there are additional benefits of becoming more physically active for participants including improvements in walking and cognitive function, weight reduction, and improvement in cardiometabolic health.

19. Risks - in nontechnical, lay language

a. List the known risks for participants as a result of participation in the research. This should not include the minimal risk of loss of confidentiality. However, it should include any physical, psychological, social, economic, and/or legal risks. If there is a greater than minimal risk of loss of confidentiality describe why this is so. Do not list risks associated with the standard-of-care procedures.

NOTE: Risks included here should be included in the consent form or information sheet, as applicable.

1. Fasting prior to bloodwork: Participants may experience a drop in blood sugar causing lightheadedness, dizziness, nausea, sweating, and shakiness as a result of fasting before their baseline and follow up visits.

2. **Blood draw: Participants may experience pain and/or bruising during venipuncture.**
 3. **DXA: A DXA scan is an x-ray scan that uses a very low-level of radiation. In this study subjects will be exposed to a very low level of radiation during the DXA scan. The radiation dose received from scans is equivalent to about 8 days natural background radiation. Background radiation is radiation normally received from sources such as cosmic rays and natural radioactivity in building materials and the ground. A small risk of cancer and other radiation effects, which may not be known at this time, may develop from each scan you receive.**
 4. **Intervention: There are risks of injury for individuals engaging in a lifestyle physical activity program after a prolonged period of inactivity. Such risks include strains, sprains, and muscle soreness, but serious physical injury such as sudden death or heart attack is considered unlikely given the screening for contra-indications via physician referral. We will attempt to reduce risks of injury and harm by promoting gradual increases in physical activity behavior across time. We will fully inform participants of the risks associated with initiating a physical activity program in the informed consent.**
 - a. **During the intervention, there is a potential risk of a participant voicing a depressed mood or verbiage of suicidal ideation. In the case that this occurs, we will provide resources for seeking mental health treatment and encourage the individual to call their primary care or mental health provider if they have one. We will write this up as an adverse event to report to the IRB.**
 5. **Symptom Measures: There are minimal risks associated with completing the patient-rated outcomes included in this protocol. All outcomes are questionnaire-based. One foreseeable risk may be psychological in that participants may experience feelings of discomfort or embarrassment when reporting on their symptoms or experiences of MS. We will fully inform participants of such risks in the informed consent.**
 6. **Physical Activity Measures: There are minimal psychological, social, or legal risks associated with completing the measures for this study. One foreseeable risk may be psychological in that non-active participants may experience some guilt, discomfort, or embarrassment with reporting inactivity. We will fully inform participants of such risks in the informed consent.**
 7. **Risk of falling: There is a risk of falling while completing the exercises.**
 8. **Risk of starting a new diet: There is a risk of feeling hungry when changing dietary patterns or reducing food intake.**
- b.** Estimate the frequency, severity, and reversibility of each risk listed.
- Risks associated with fasting prior to blood draw are typically rapidly reversible upon ingesting food and drink or lying down and should not result in severe harm to the participant. Discomfort associated with venipuncture is rapidly reversible. Bruises from venipuncture will heal in several days. The risks associated with other testing may occur in 5% of subjects, and are preventable/reversible through clear instructions and strategies for remediation as outlined above. Risks associated with changing dietary habits are typically mild and reversible within 1-2 weeks.**
- c.** Is this a therapeutic study or intervention? Yes No
- If Yes, complete i.-iii.
- i. Describe the standard of care in the setting where the research will be conducted: _____
 - ii. Describe any other alternative treatments or interventions: _____
 - iii. Describe any withholding of, delay in, or washout period for standard of care or alternative treatment that participants may be currently using: _____

d. Do you foresee that participants might need additional medical or psychological resources as a result of the research procedures/interventions? Yes No

If Yes, describe the provisions that have been made to make these resources available. _____

e. Do the benefits or knowledge to be gained outweigh the risks to participants? Yes No

If No, provide justification for performing the research: _____

20. Precautions/Minimization of Risks

a. Describe precautions that will be taken to avoid risks and the means for monitoring to detect risks.

Intervention: We will attempt to reduce risks of injury and harm by promoting gradual increases in physical activity behavior across time. We will fully inform participants of the risks associated with initiating a physical activity program in the informed consent. We will obtain physician approval to participate prior to enrollment in the study.

Symptom Measures: One foreseeable risk may be psychological in that participants may experience feelings of discomfort or embarrassment when reporting on their symptoms or experiences of MS. We will fully inform participants of such risks in the informed consent.

Physical Activity Measures: There are minimal psychological, social, or legal risks associated with completing the measures for this study. One foreseeable risk may be psychological in that non-active participants may experience some guilt, discomfort, or embarrassment with reporting inactivity. We will fully inform participants of such risks in the informed consent.

Participants will be asked a set of questions each week to assess their general health (see attached Adverse Event form). If a participant reports any notable changes for 2 consecutive weeks, that information will be given to [name] for review.

Any serious adverse events will be promptly reported to the Institutional Review Board at UAB. Safety reports will be sent to the PI from the intervention staff, or data collection staff if the event occurs during baseline/follow up testing. The PI will be responsible for reviewing the data with [name].

If the protocol involves drugs or devices skip Items 20.b. and 20.c. and go to Item 21. Instead include this information in the [Drug Review Sheet](#) or [Device Review Sheet](#), as applicable.

b. If hazards occur to an individual participant, describe (i) the criteria that will be used to decide whether that participant should be removed from the protocol; (ii) the procedure for removing such participants when necessary to protect their rights and welfare; and (iii) any special procedures, precautions, or follow-up that will be used to ensure the safety of other currently enrolled participants.

The PIs will monitor protocol adherence. Throughout the study, study staff will inform the PIs of adverse events. Events determined by the PIs and [name] to be unanticipated serious problems involving risks to subjects will be reported by the PI to the IRB within 5 working days of occurrence. Non-serious adverse events will be reported per IRB policy at the time of continuing review. If any protocol changes are needed as a result of an adverse event, the PI will submit a modification request to the IRB. Protocol changes will not be implemented prior to IRB approval.

c. If hazards occur that might make the risks of participation outweigh the benefits for all participants, describe (i) the criteria that will be used to stop or end the entire protocol and (ii) any special procedures, precautions, or follow-up that will be used to ensure the safety of currently enrolled participants.

If the risks involved in participating appear to exceed the benefits during review of occurrences of serious adverse events, the PIs will consult with the complete investigator team to decide to

terminate the study. If the study is terminated, participants will be given information related to the study risks that may have affected them or their health.

21. Informed Consent

a. Do you plan to obtain informed consent for this protocol? Yes No

If Yes, complete the items below.

If No, complete and include the [Waiver of Informed Consent](#) or [Waiver of Authorization and Informed Consent](#), as applicable.

b. Do you plan to document informed consent (obtain signatures) for this protocol? Yes No

If Yes, complete the items below.

If No, complete the items below and include the [Waiver of Informed Consent Documentation](#).

c. How will consent be obtained?

The recruitment coordinator at Lakeshore Foundation and all intervention staff who will be recruiting participants will be knowledgeable of the purposes of the study. Once interest is determined, the recruitment coordinator or intervention staff will provide a detailed description of the study, screen the participant for eligibility, answer any questions, and if appropriate, schedule their first visit. At the beginning of the first visit, consent will be obtained prior to any testing.

d. Who will conduct the consent interview?

The recruitment coordinator at Lakeshore Foundation or the project coordinator.

e. Who are the persons who will provide consent, permission, and/or assent? **Study participants**

f. What steps will be taken to minimize the possibility of coercion or undue influence?

Participants will be self-referred. As described above, the consent form will be carefully reviewed with participants. Further, they will have 24 hours to consider participation in the study.

g. What language will the prospective participant and the legally authorized representative understand?

English

h. What language will be used to obtain consent? **English**

i. If any potential participants will be, or will have been, in a stressful, painful, or drugged condition before or during the consent process, describe the precautions proposed to overcome the effect of the condition on the consent process. If not, enter "None." **None**

j. If any protocol-specific instruments will be used in the consenting process, such as supplemental handouts, videos, or websites, describe these here and provide a copy of each. If not, enter "None." **None**

k. How long will participants have between the time they are told about the protocol and the time they must decide whether to enroll? If not 24 hours or more, describe the proposed time interval and why the 24-hour minimum is neither feasible nor practical. **A minimum of 24 hours**

22. Procedures to Protect Privacy

Describe how you will protect the privacy interest of the participants. Include how you will make sure others cannot overhear your conversation with potential participants and that individuals will not be publicly identified or embarrassed. **There will be a password protected link between data and the participant's name during this study, but this link will be destroyed upon study completion. We will retain screening data for those who qualify and volunteer to participate, and destroy screening data from those who do not qualify or do not volunteer.**

23. Procedures to Maintain Confidentiality

a. Describe how you will store research data to maintain confidentiality (both paper records and electronic data), including how access is limited. If data will be stored electronically anywhere other than a server

maintained centrally by UAB, identify the department and all computer systems used to store protocol-related data. All participants will be assigned an identification number and all data collection, as well as data analyses, will be conducted with the coded non-identifiable data. All data will be kept in a locked file cabinet and only aggregated data will be used for presentation or publication purposes. There will not be a link between the identification number and participant for purposes of tracking participants over time. We will not maintain a link between identification number and the subject's name after completion of the study procedures, and there is no intention of linking data collected in the current project with data collected in another project. We will retain screening data for those who qualify and volunteer, and destroy the screening data for those who are excluded or do not volunteer.

- b. Will any data from this protocol be given to any person, including the subject, or any group, including coordinating centers and sponsors? Yes No
- If Yes, complete i-iii.
- i. Who will receive the data? _____
- ii. What data will be shared? _____
- iii. How will the data be identified, coded, etc.? _____

24. Genomic Data Sharing (GDS)

Researchers who collect genomic data as part of a NIH grant funded after January 25, 2008 may be required to submit those data to a NIH database for broad scientific sharing. See [Genomic Data Sharing](#) in the IRB Guidebook for more information.

- a. Does this protocol involve the proposed submission of genetic data into genomic repositories created to share genetic information for research purposes? Yes No
- b. Will UAB be uploading the final genomic data to the central repository (e.g., dbGaP)? Yes No
- If Yes to both a and b, submit a Detailed Data Sharing Plan to the IRB for review. This plan should include any known data use limitations and indicate whether aggregate-level data are appropriate for general research use. For guidance see the [NIH Genomic Data Sharing Policy](#).
- c. Submit a copy of the NIH Institutional Certification Form.
- To determine which certification form to include, answer i-ii.
- i. Was this protocol funded prior to January 25, 2015? Yes No
- If yes, and consent will be obtained, submit the [Extramural Institutional Certification - Before January 25 - With Consent](#).
 - If yes, and consent will not be obtained, submit the [Extramural Institutional Certification - Before January 25 - Without Consent](#).
- ii. Was this protocol funded after January 25, 2015? Yes No
- If yes, submit the [Extramural Institutional Certification - After January 25](#).

25. Additional Information

In the space below, provide any additional information that you believe may help the IRB review the proposed research, or enter "None." None.

Analysis plan

Planned: We will explore descriptive statistics including means, standard deviations, and confidence intervals for all variables. Aim 1 and Aim 2 are similar from the perspective of data analysis. We will use mixed-factor ANOVA to determine differences in outcomes over time by group. There will be no adjustment for multiple testing of outcomes because the goal of this study is to collect preliminary data. Data collected for feasibility will mostly be descriptive. The data will be summarized for guidance in designing the main trial supported by this pilot study.

Actual: Due to small sample which led to early termination, only descriptive statistics for each group were analyzed.

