 - 9. Questionnaires: Symptoms of fatigue, depression, anxiety, and pain will be measured by the Fatigue Severity Scale (FSS), Modified Fatigue Impact Scale (MFIS), Hospital Anxiety and Depression Scale (HADS), and short-form McGill Pain Questionnaire (SF-MPQ) respectively. The FSS is a 9-item unidimensional measure of fatigue and its disabling consequences over the past week in medical populations including MS. The MFIS is a 21-item measure of physical, cognitive, and psychosocial impact of fatigue on daily life over the past 4 weeks. The HADS contains 14 items that measure the frequency of anxiety and depressive symptoms over the past week. The SF-MPQ has a 15-item adjective checklist that captures sensory and affective dimensions of pain experienced over the past week. These variables will be measured at baseline, 8 and 16 weeks.**
 - 10. Dietary adherence: Participants will be asked to will complete three 24 hour dietary phone recalls over a 14 day period. These calls will be unannounced and participants will be informed that they will be asked to recall all they consumed within the last 24 hours at the time of the call. They will receive two of the three recall phone calls during the week, and one on a Monday morning to capture a weekend recall. Research staff will follow standard protocols for performing a 24 hour food recall and study staff will provide participants with materials at baseline to help them answer the food recall questions. Participants will receive three more 24 hour dietary recall phone calls at the 16 week mark.**

At the end of the baseline visit, research staff will give the participant information for accessing the questionnaires on-line. Participants will be given the option to complete the questionnaires while at the visit or at home. Participants will be given an accelerometer to wear for 14 days, along with a pre-stamped envelope and instructions to mail back the accelerometer after the 14 days. Participants will also receive instructions on for completing the 24 hour dietary recall phone calls. All participants will receive a take home folder containing instructions for the two weeks following baseline as well as information for depression in individuals with MS, provided by the National MS Society.

At 14 days after baseline, staff will contact participants to remind them to return their accelerometer via mail, complete any questionnaires that have not been completed, and to schedule their first coaching appointment.

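### Does a physical-activity forum given to both arms let enough diet advice reach the comparison arm to require a change?

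*Combined protocol and SAP*

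**What the plan says.** All places are in the combined protocol and SAP.

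- **Forum.** Section 17.a, part III, item 1 (BIPAMS Website) lists an ongoing, seeded forum "for discussions of physical activity behavior change amongst participants (i.e., another form of vicarious experience".
- **Who gets it.** The same item then says: "In addition to these intervention aspects, which all participants will receive, the BIPAMS+Diet group will access additional information beginning in Week 9". The forum is therefore part of both arms' programme.
- **When the arms diverge.** Part III states: "At the completion of the eighth week, participants will receive their randomization assignment". The diet components run from week 9 to week 16.
- **Diet arm.** Item 1 gives this arm a calorie prescription and dietary goals, discussed in the video chats. It also says: "Participants will receive nutrition education content via the BIPAMS website". Item 2 adds food logging in an app.
- **Comparison arm.** "Participants in the BIPAMS group will be given a single link to healthy eating resources for people with MS", and beyond that "no other healthy eating content will be given and no individualized recommendations or goals will be given related to nutrition".
- **Measurement.** Dietary recalls, bloodwork, DXA and anthropometrics are each done twice (part II and the procedure table in section 17). At week 8, "Participants will not be asked to come into the lab at this point". The symptom questionnaires are the exception: "These variables will be measured at baseline, 8 and 16 weeks".
- **Size and analysis.** Section 16.e plans 12 per arm. The analysis plan under section 25 describes preliminary data to guide a main trial. It reports that the study ended early and that only descriptive statistics by group were produced.

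**The concern.** The plan sets a clear ceiling on the comparison arm's diet exposure: one link and nothing individual. It also gives both arms a peer channel and describes no safeguard for that ceiling. After week 8, members of the diet arm are learning about fruit, vegetables, lean protein and snacks on the same website. Nothing in the document says that they and the comparison arm use separate forums, that posts are moderated, that participants are asked not to share diet material, or that posts are logged.

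Diet plus activity against activity alone is the only randomized comparison. If comparison participants picked up peer advice and changed their diet in the intended direction, the difference between arms would move toward zero. No recording of forum exposure is described, so no adjustment at analysis is available from what is written. A main trial that copied the arrangement would carry the same dilution.

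**Working it through.** **Reading the text.** There is no stated figure to reproduce: the document gives no effect size, SD, power or sample-size calculation. Four points follow from setting the sections side by side.

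1. The forum goes to both arms. One shared instance is the natural reading, but it is not stated outright.
2. The stated topic is physical activity, so a diet post would be off-topic. Seeding implies some staff presence, though not moderation.
3. Diet content reaches one arm on a common website, which implies some arm-specific access. The forum is not mentioned in that connection.
4. The calorie prescription, app logging and coached dietary goals are individual. Only general tips could pass, and the comparison arm already has general healthy-eating material through its link.

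Diet tips read before assignment could persist to week 16 even though the laboratory measures and recalls have no week-8 value. Because such exposure precedes knowledge of the arm, it would be expected to fall equally on both arms.

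**Scale of dilution (all inputs assumed except 12 per arm).** Let f be the share of the comparison arm acting on tips and g the share of the diet effect each of them gains.

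- Shrinkage of the contrast = f × g.
- Loss for an assumed 0.5 SD effect = 0.5 × f × g.
- Sample-size factor for equal power = 1/(1 − f × g)².

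| f | g | Shrinkage | Loss (SD) | Sample-size factor |
|---|---|---|---|---|
| 1/12 | 0.10 | 0.83% | 0.004 | 1.02 |
| 1/12 | 0.25 | 2.08% | 0.010 | 1.04 |
| 3/12 | 0.10 | 2.5% | 0.013 | 1.05 |
| 3/12 | 0.25 | 6.25% | 0.031 | 1.14 |
| 6/12 | 0.10 | 5.0% | 0.025 | 1.11 |
| 6/12 | 0.25 | 12.5% | 0.063 | 1.31 |

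**Precision of this pilot.** The 95% half-width of a between-arm mean difference, in SD units, is t(0.975, 2n − 2) × √(2/n).

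- n = 12 per arm (planned): 2.074 × 0.408 = 0.847
- n = 10 per arm (assumed completers): 0.940
- n = 8 per arm (assumed completers): 1.072

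The largest loss in the table is 0.0625/0.847 = 7% of the half-width at full enrolment.

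**Could the planned data detect it?** The recalls at baseline and week 16 would show diet change in the comparison arm, and the analysis plan already provides confidence intervals for every variable. With 12 participants, the half-width for mean change is t(0.975, 11)/√12 = 0.635 SD of change. Any change seen would also include the run-in and use of the supplied link, so it could not be attributed to the forum.

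**The case for a change.** The strongest case for a change runs as follows. The protocol treats the forum as an active ingredient that shapes behaviour through others' example. Eligible participants have a BMI of 25 or more and follow no specific health diet, so they have room to respond to a tip. A stated topic is not a control. The pilot exists to inform a main trial, where the top of the assumed range would raise the sample size by 31%, while a sentence on forum access costs almost nothing.

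Part of this stands. The document is silent on access and moderation, and the route is possible. The rest does not amount to a fault in the plan:

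- Nothing indicates that diet posts occurred or were expected. The 31% needs half the comparison arm to gain a quarter of the full diet effect from informal posts, although the prescription, logging and coaching cannot pass that way.
- Section 17 is an ethics-form section asked for in lay language. Forum permissions and moderation rules would not necessarily appear there, and staff running a physical-activity forum can reasonably be expected to keep it on topic.
- Splitting the forum by arm is a trade-off. It leaves at most 12 users in each part, reduces peer exchange on activity, and without moderation would let the diet arm form a diet peer-support group that the other arm lacks. If entry is staggered (assumed), participants still in run-in would also need a place.
- The pilot has ended, so its forum rules can no longer be altered.

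**Conclusion.** No change to the plan follows. The document leaves unsaid whether the forum is shared, split or moderated after week 8, and informal diet tips could in principle reach the comparison arm. This is a gap in operational detail that study staff would sensibly fill by holding the forum to its stated physical-activity topic.

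The size of any dilution cannot be derived from the document. Under the assumed ranges (1 to 6 of 12 participants, 10% to 25% of the effect each) it is 0.8% to 12.5% of the contrast. For an assumed 0.5 SD effect that is 0.004 to 0.063 SD, against a half-width of 0.85 SD or more. It would not have been visible in this pilot, which was reported descriptively. The point is worth one clarifying sentence if the same website is used in the main trial; it does not show that any stated rule or analysis here is wrong.
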